5.2 Exclusion Criteria

Subjects will be excluded from enrolling in the trial if they meet any of the following exclusion criteria:

1. Subjects with *HER2/neu*-positive immunohistochemistry 3+ or fluorescence in situ hybridization-amplified breast tumors who are eligible for, but who have not received HER2-targeted therapy (eg, trastuzumab)
2. Concomitant anticancer therapies (eg, endocrine therapy for breast cancer)
3. Prior therapies discontinuation periods:
 - a) Radiation within 3 weeks of enrollment
 - b) Chemotherapy within 4 weeks of enrollment
 - c) Nitrosoureas within 6 weeks of enrollment
 - d) Biologic therapy and/or immunomodulatory therapy (eg, granulocyte colony stimulating factor [G-CSF]/granulocyte macrophage colony stimulating factor [GM-CSF], interferons or interleukins, growth hormone, intravenous immunoglobulin [IVIG], retinoic acid), check point inhibitors (eg, ipilimumab, anti-PD-1 or anti-PDL-1 antibodies) within 6 weeks of enrollment
 - e) No washout period is required for endocrine therapy
4. Radiation therapy encompassing $>25\%$ of bone marrow
5. History of bone marrow or stem cell transplantation
6. Any congenital or acquired condition leading to an inability to generate an immune response, including concomitant immunosuppressive therapy
7. Immunosuppressive therapy:

- a) Systemic immunosuppressive drugs including corticosteroids (prednisone equivalent >10 mg/day, <http://www.medcalc.com/steroid.html>) within 6 weeks
- b) Immune suppression/requiring immunosuppressive drugs, including subjects with organ allografts
- c) Active autoimmune disease requiring the equivalent of >10 mg/day of prednisone

8. Major surgery within 4 weeks of study treatment, or major surgery planned for duration of study participation

9. History of prior malignancy, unless the prior malignancy was diagnosed and definitively treated ≥ 5 years previously with no subsequent evidence of recurrence

NOTE: This does not apply to previous breast cancer, carcinoma in situ of the cervix, inactive melanoma or non-melanoma skin cancer, or Grade 1 papillary bladder cancer

10. Subjects with brain or subdural metastases are not eligible, unless local therapy completed and corticosteroids discontinued for this indication for ≥ 4 weeks before starting study treatment. Any signs (eg, radiologic) and/or symptoms of brain metastases must be stable for ≥ 4 weeks before starting study treatment; radiographic stability should be determined by comparing a contrast-enhanced computed tomography (CT) or magnetic resonance imaging (MRI) brain scan performed during screening to a prior scan performed at least 4 weeks earlier.

NOTE: Screening for brain lesions by CT or MRI is not required for all potential subjects; however, if there are any neurological signs or symptoms consistent with brain metastases, then a brain CT or MRI should be performed as clinically indicated.

11. Any medications that induce, inhibit or are substrates of cytochrome P450 (CYP450) 3A4 within 7 days prior to the first dose of study drug

12. Subjects with meningeal carcinomatosis

13. Known significant hypersensitivity to study drugs or excipients

14. History of malabsorption syndrome or other condition that would interfere with enteral absorption

15. International Normalized Ratio (INR) and activated PTT $< 1.5 \times$ ULN, if not therapeutically anticoagulated. Subjects who are being therapeutically anticoagulated with an agent such as Coumadin (warfarin sodium) or subcutaneous heparin may be included provided there is no prior evidence of underlying abnormality in coagulation parameters, screening test results are in appropriate therapeutic range, and anticoagulation regimen is stable and closely monitored

16. New York Heart Association (NYHA) Class II or greater congestive heart failure OR active ventricular arrhythmia requiring medication

17. Any other unstable or clinically significant concurrent medical condition (eg, infection requiring systemic anti-infective agents) that would, in the opinion of the investigator, jeopardize the safety of a subject and/or their compliance with the protocol

18. Localized infection at site of injectable lesion(s) requiring anti-infective therapy within 2 weeks of the first dose of study drug

NOTE: Appropriate testing (eg, punch biopsy [PBx] with bacterial counts) must be performed to rule out infection in cases where the presence of infection is ambiguous or clinical signs of infection are evident.

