	
generate an immune response, including concomitant immune suppressive therapy
 
7. Immunosuppressive therapy:
 
a) Systemic immunosuppressive drugs including corticosteroids (prednisone equivalent >10 mg/day, http://www.medcalc.com/steroid.html) within 6 weeksb) Immune suppression/requiring immunosuppressive drugs, including subjects with organ allograftsc) Active autoimmune disease requiring the equivalent of >10 mg/day of prednisone 
8. Major surgery within 4 weeks of study treatment, or major surgery planned for duration of study participation
 
9. History of prior malignancy, unless the prior malignancy was diagnosed and definitively treated ≥ 5 years previously with no subsequent evidence of recurrence
 
NOTE: This does not apply to previous breast cancer, carcinoma in situ of the cervix, inactive melanoma or non-melanoma skin cancer, or Grade 1 papillary bladder cancer
 
10. Subjects with brain or subdural metastases, unless local therapy has completed and corticosteroids have been discontinued for this indication for ≥ 4 weeks before starting study treatment. Any signs (eg, radiologic) and/or symptoms of brain metastases must be stable for ≥ 4 weeks before starting study treatment; radiographic stability should be determined by comparing a contrast-enhanced computed tomography (CT) or magnetic resonance imaging (MRI) brain scan performed during screening to a prior scan performed at least 4 weeks earlier.
 
11. Any medications that induce, inhibit, or are substrates of cytochrome P450 (CYP450) 3A4 within 7 days prior to the first dose of study drug
 
12. Subjects with meningeal carcinomatosis
 
13. Known significant hypersensitivity to study drugs or excipients
 
14. History of malabsorption syndrome or other condition that would interfere with enteral absorption
 
15. International Normalized Ratio (INR) and activated partial thromboplastin time [PTT] $<1.5 \times$ ULN, if not therapeutically anticoagulated. Subjects who are being therapeutically anticoagulated with an agent such as Coumadin (warfarin sodium) or subcutaneous heparin may be included provided there is no prior evidence of underlying abnormality in coagulation parameters, screening test results are in appropriate therapeutic range, and anticoagulation regimen is stable and closely monitored.
 
16. New York Heart Association (NYHA) Class II or greater congestive heart failure OR active ventricular arrhythmia requiring medication

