5.1 Inclusion Criteria

To be enrolled in the trial, each subject must satisfy all of the following inclusion criteria:

1. Males or females of all races \geq 18 years of age, who have provided written informed consent prior to completing any study-specific procedure.
2. Histologically or cytologically confirmed adenocarcinoma of the breast, either locally recurrent or metastatic disease with injectable lesions, for which no proven curative therapy exists. Locally recurrent disease must not be amenable to surgical resection or radiation with curative intent.
3. Subject has failed or progressed on at least 1 prior systemic chemotherapy regimen \pm biologic/experimental therapy (if first-line therapy, failure or progression during or within the first 30 days).
4. Resolution of all chemotherapy or radiation-related toxicities to Grade 1 severity or lower, except for stable sensory neuropathy \leq Grade 2 and alopecia.
5. A minimum of 2 lesion(s) assessed by imaging using mRECIST v1.1. 1 or more lesions NOT to be injected AND at least 1 injectable lesion(s) (eg, may use radiographically-guided injection of lesions if available at site)
6. Eastern Cooperative Oncology Group (ECOG) performance status 0, 1, 2
7. Male and female subjects must agree to use a highly reliable method of birth control (expected failure rate less than 5% per year) from the screening visit through 28 days after the last dose of study drug. Women of childbearing potential (perimenopausal

women must be amenorrheic for at least 12 months to be considered of non-childbearing potential) must have a negative pregnancy test at screening.

8. Adequate bone marrow reserve as indicated by:
 - a) Absolute neutrophil count (ANC) $> 1500/\mu\text{L}$ (without use of growth factors within 7 days)
 - b) Absolute lymphocyte count (ALC) $> 700/\mu\text{L}$ (without use of growth factors within 7 days)
 - c) Platelet count $> 100,000/\text{mm}^3$ (without transfusion in prior 7 days)
 - d) Hemoglobin $> 9.0 \text{ g/dL}$ (without transfusion in prior 7 days)
9. Adequate renal function as evidenced by eGFR using the Modification of Diet in Renal Disease (MDRD) equation: $\text{eGFR} \geq 60 \text{ mL/min}/1.73 \text{ m}^2$
10. Adequate liver function as evidenced by the following:
 - a) Bilirubin ≤ 1.5 times the upper limits of normal (ULN)
 - b) ALT and AST $\leq 2.5 \times \text{ULN}$, in the case of liver metastases $\leq 5 \times \text{ULN}$

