6.2.5 Retreatment Criteria, Dose Delays and Modifications

Subjects may receive up to 6 cycles of study drug treatment. To receive each repeat treatment cycle, all treatment-related AEs must have resolved to Grade 1 or baseline and the following laboratory criteria must be met:

Hemoglobin \geq 9 g/L	eGFR \geq 60 mL/min/1.73 m ²
Lymphocytes $>$ 700/ mm ³	AST and ALT \leq 2.5 x ULN For subjects with documented liver metastases, ALT and AST \leq 5 \times ULN
Neutrophils \geq 1,500/ mm ³	Total bilirubin $<$ 1.5 x ULN
Platelets \geq 100,000/ mm ³	INR and PTT $<$ 1.5 x ULN

Clinical laboratory tests drawn pre-treatment for analysis on Day 1 of each cycle may be used for determining if the re-treatment criteria have been met, and must be reviewed by the investigator or designee prior to the next cycle of study drug administration. Two treatment delays for recovery to acceptable levels are allowed at weekly intervals up to a maximum of 14 days. In the event that a treatment-related dose delay is necessary for palifosfamide, then the next cycle of study treatment will be administered at 80% of the dose ([Table 3](#)). If an AE is clearly related to 1 study drug and not the other (in combination Treatment Arm C), then dose modification/delay is to occur for the relevant study drug (INXN-1001 and/or palifosfamide). A maximum of two dose reductions, of either INXN-1001 or palifosfamide, will be allowed.

Table 3. Dose Modifications for Palifosfamide-related Toxicity^a

ADVERSE EVENT	PALIFOSFAMIDE
Hematologic	
Platelet count <100 × 10 ⁹ /L	Delay dose of palifosfamide up to 14 days until platelet count ≥ 100 × 10 ⁹ /L, then reduce by 20%.
ANC < 1500/mm ³	Delay dose of palifosfamide up to 14 days until ANC returns to ≥ 1500, then maintain dose when restarted.
Neutropenic fever	Delay dose of palifosfamide up to 14 days until resolved, then reduce by 20%.
Any Grade 4 hematologic toxicity	Delay dose of palifosfamide up to 14 days until Grade ≤ 1 or baseline, then reduce by 20%.
Estimated Glomerular Filtration Rate (eGFR) (Appendix 5)	
≥25% up to <50% decrease from baseline ^b	Hold dose until repeat test is performed. Reduce dose of palifosfamide by 20% if confirmed on repeat test.
≥50% decrease from baseline ²	Hold dose until repeat test is performed. Discontinue palifosfamide if confirmed on repeat test.
Non-hematologic (other than creatinine or urinary electrolyte wasting)	

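### Exclusion criterion 15 is inverted as written: it bars non-anticoagulated subjects with INR and PTT both below 1.5 × ULN and admits those with a raised value

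*Protocol*

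**What the plan says.** Protocol 5.2 opens with the rule "Subjects will be excluded from enrolling in the trial if they meet any of the following exclusion criteria". Item 15 beneath it is "International Normalized Ratio (INR) and activated PTT $< 1.5 \times$ ULN, if not therapeutically anticoagulated". The Synopsis lists the same item among its exclusions, with the same sign: "International Normalized Ratio (INR) and activated partial thromboplastin time [PTT] $<1.5 \times$ ULN, if not therapeutically anticoagulated". In both places the item goes on to allow subjects on therapeutic anticoagulation to enter, provided that there is no underlying coagulation abnormality, that screening values are in the therapeutic range, and that the regimen is stable and closely monitored.

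Protocol 6.2.5 sets the laboratory conditions for each repeat cycle. Its coagulation row is "INR and PTT $<$ 1.5 x ULN", with no exception for anticoagulated subjects. Its haemoglobin row, in the text as extracted, is "Hemoglobin \geq 9 g/L". The entry limit in 5.1, item 8d, is "Hemoglobin $> 9.0 \text{ g/dL}$ (without transfusion in prior 7 days", and the Synopsis gives the same limit and unit.

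The inclusion criteria contain no coagulation limit. The SAP contains no laboratory limits for eligibility or re-dosing.

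**The concern.** A value below 1.5 × ULN is the acceptable range, yet it stands in a list of reasons to exclude. Applied as printed, item 15 turns away subjects with normal clotting and accepts those with a raised INR or PTT.

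Item 15 is the only numeric coagulation limit at entry, and treatment is an intratumoral injection, given by multiple needle passes, in each of up to 6 cycles. Protocol 6.1.2 requires each criterion to be reviewed and documented in the CRF, at about 30 centers. A site that follows the text and a site that follows the evident intent would record opposite answers for the same subject. Major protocol violations are to be summarized by arm (8.6.1), so the error could also reach the deviation tables.

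**Working it through.** No sample-size figure is in dispute. The check sets the limits side by side.

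**Step 1: item 15 against the 6.2.5 row, for subjects not anticoagulated.** Values are multiples of ULN.

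- Item 15 as printed: excluded if INR < 1.5 and PTT < 1.5.
- Evident intent: excluded if INR ≥ 1.5 or PTT ≥ 1.5.
- 6.2.5: re-dosing allowed only if INR < 1.5 and PTT < 1.5.

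| INR | PTT | Excluded as printed | Excluded as intended | Re-dosing allowed |
|---|---|---|---|---|
| 1.0 | 1.0 | yes | no | yes |
| 1.4 | 1.4 | yes | no | yes |
| 1.6 | 1.0 | no | yes | no |
| 1.0 | 1.6 | no | yes | no |
| 2.0 | 2.0 | no | yes | no |

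The printed exclusion and the re-dosing condition are the same set. Anyone admitted by the printed text fails the re-dosing row unless the raised value falls. Under the intended rule, entry and re-dosing agree in every line.

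**Step 2: every 6.2.5 row against its entry limit.**

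| Row | Entry | 6.2.5 | Ratio | Same direction |
|---|---|---|---|---|
| eGFR (mL/min/1.73 m²) | ≥ 60 | ≥ 60 | 1.0 | yes |
| Lymphocytes (per µL = per mm³) | > 700 | > 700 | 1.0 | yes |
| AST/ALT (× ULN; liver metastases) | ≤ 2.5; ≤ 5 | ≤ 2.5; ≤ 5 | 1.0; 1.0 | yes |
| Neutrophils (per µL = per mm³) | > 1500 | ≥ 1500 | 1.0 | yes |
| Bilirubin (× ULN) | ≤ 1.5 | < 1.5 | 1.0 | yes |
| Platelets (per mm³) | > 100,000 | ≥ 100,000 | 1.0 | yes |
| INR/PTT (× ULN) | < 1.5, as an exclusion | < 1.5, as a condition | 1.0 | no |
| Haemoglobin (g/dL) | > 9.0 | ≥ 0.9 | 0.1 | yes |

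The haemoglobin conversion is 9 g/L ÷ 10 = 0.9 g/dL, and 0.9 / 9.0 = 0.1. Six of the eight rows repeat the entry number in the same direction, differing at most in whether the limit itself passes. The two that break the pattern are INR/PTT and haemoglobin.

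**Step 3: the anticoagulation allowance.** Item 15 exempts stable anticoagulated subjects from the limit at entry, but the 6.2.5 row does not. A subject admitted under the allowance whose value is at or above 1.5 × ULN could receive Cycle 1 and would then fail the row for every later cycle while the value stayed there. Reversing item 15 alone leaves this mismatch in place.

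**The case against.** The strongest reply is that nobody would apply item 15 literally. Its second sentence makes sense only if the first was meant as an entry requirement, and 6.2.5 shows the direction. The list already holds another line that cannot work as an exclusion (3e, on endocrine washout). Exclusion 17 lets the investigator keep out a subject with an unsafe condition, and registration is central. All of this stands and limits the practical harm. None of it corrects the printed rule, which appears in two separately worded copies, so a PDF-reading fault is unlikely.

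On haemoglobin, the reply is stronger. The g/L unit appears once, in a table read from PDF by a program, and the amendment summary for that section does not reprint the table. A reader might infer that two safety thresholds are firmly wrong. The documents support that for item 15 only; the mismatch in step 2 makes a slip likely but cannot show whether it lies in the protocol or in the reading of it.

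A reader might also infer that severely anaemic subjects could be re-dosed freely. That goes too far even if g/L is genuine. Section 6.2.5 requires treatment-related AEs to have resolved to Grade 1 or baseline, generally stops treatment after a related Grade 4 AE, and has laboratory results reviewed before each cycle. Table 3 delays palifosfamide for Grade 4 haematologic toxicity, although its title confines it to palifosfamide-related toxicity. What would lack a working numeric limit is anaemia judged unrelated to treatment: at any grade in Arm A, and at least below Grade 4 in Arm C.

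**Conclusion.** Wrong as written, on item 15. The error is one of direction: for non-anticoagulated subjects the printed rule gives the opposite of the intended answer for every pair of values, and it contradicts 6.2.5. Confidence is high, because both copies carry the same sign under an exclusion heading and no other text corrects it. The realistic consequence is inconsistent eligibility records and deviations. A reader might infer that subjects with abnormal clotting would actually be enrolled in place of normal ones; the documents do not support that, given the recoverable intent and central registration. They give no figures on how many subjects could be affected.

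The haemoglobin point is secondary and depends on the source file. If the unit there is g/dL, it falls away.

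Sample size, power and alpha are unaffected: the two-stage rules in 8.1 use only counts progression-free at week 16, and the analysis populations in 8.3 do not depend on meeting these criteria.

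**What to change.** 1. In the Synopsis and in 5.2, reword item 15 so that a subject not on therapeutic anticoagulation is excluded when INR **or** activated PTT is ≥ 1.5 × ULN. The change from *and* to *or* matters, since one raised test should suffice. Keep the anticoagulation sentence as it is.
2. Add the same anticoagulation exception to the INR/PTT row in 6.2.5, so that subjects admitted on stable anticoagulation are not barred from re-dosing.
3. Check the haemoglobin unit in 6.2.5 against the source file. If it reads g/L, change the row to ≥ 9 g/dL; if it reads g/dL, do nothing.

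The cost is a few one-line text changes in a short protocol amendment, with no effect on sample size or analysis.

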5.3 Withdrawal of Subjects from Study Treatment and/or Study

The investigator and/or the subject have the right to terminate the subject's participation in the study at any time. Subjects who discontinue study drug should complete the Post-Treatment Safety Assessment visit.

A subject **may** withdraw (or be withdrawn) from the study treatment prematurely for any of the following reasons:

- PI determines further participation is not in subject's best interest.
- Clinically significant disease progression

NOTE: In the absence of rapid clinical deterioration, disease progression should be confirmed by a repeat, consecutive assessment no less than 4 weeks from the date first documented to ensure that more slowly declining total tumor burden in response to therapy is not missed.

A subject **MUST** be withdrawn in the event of any of the following:

- Withdrawal of informed consent.
Note: Any subject who wishes to withdraw from the study treatment may do so but will be counseled that follow-up for the effects of immunotherapy is strongly recommended.
- Any treatment-related AE meeting withdrawal criteria.
- Substantial noncompliance with the requirements of the study.
- Subjects with a confirmed positive pregnancy test.
- Any intercurrent illness that would, in the judgement of the investigator, affect assessments of clinical status to a significant degree and require discontinuation of protocol therapy.

Every effort should be made to follow subjects who withdraw from study treatment with ongoing treatment-related AEs in order to determine the outcome of the event.

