Not treatment-related Grade 3 if unresponsive to appropriate therapy.	Delay dose of palifosfamide for up to 14 days until Grade ≤ 1 or baseline, then reduce by 20%.
Not treatment-related Grade 4	Delay dose of palifosfamide up to 14 days until ≤ Grade 1 or baseline, then reduce by 20%.

^aWhen indicated, the maximum permitted delay of study drug administration due to toxicity and/or for confirmatory laboratory testing is 14 days.

^bBaseline eGFR determined based on the most recent serum creatinine measurement prior to study drug administration (ie, Cycle 1 Day 1 or Screening).

Subjects who experience a treatment-related Grade 4 AE, other than nausea and/or vomiting in the absence of optimal treatment with antiemetics, will be discontinued from study treatment. If, however, the subject has experienced a substantial benefit from treatment and the PI and Medical Monitor recommend continuation on the study, re-exposure to the experimental treatment may proceed on a case-by-case basis.

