6.2.6 Severity Grading and Management of Injection Site Reactions

Injection of a biologic agent carries a potential risk of injection site reaction which is characterized as an intense reaction (usually immunologic) at or near the site of injection. Injection reactions will be graded according to the NCI CTCAE v4.03.

Table 4 outlines the injection site reaction grading system, associated symptoms, and the recommended actions to be taken. Reactions at the INXN-2001 injection site that occur within 24 hours after the injection and are attributed to INXN-2001 will be considered to be injection-related AEs.

Table 4. Injection Site Reaction Severity Grading and Management

CTCAE Grade	Symptoms	Course of Action
1	Tenderness with or without associated symptoms (e.g., warmth, erythema, itching)	No intervention required.
2	Pain; lipodystrophy; edema; phlebitis	Proceed with further dosing cycles.
3	Ulceration or necrosis; severe tissue damage; operative intervention indicated	Discontinue further study treatment and notify Medical Monitor. If toxicity meets seriousness criteria, immediately report as per SAE reporting procedures; see Section 8.4 .
4	Life-threatening consequences; urgent intervention indicated	Permanently discontinue study treatment and notify Medical Monitor. Defaults to “serious”. Immediately report as per SAE reporting procedures; see Section 8.4 .
5	Death	Immediately notify Medical Monitor and report as per SAE reporting procedures; see Section 8.4 . Discontinue further subject enrollment.

As with all AEs, injection-related signs or symptoms which, in the Investigator’s judgment, are not related to immunologic reactions should be recorded and graded as AEs according to NCI CTCAE v.4.03 criteria in the CRF. Study stopping rules will not apply to a specific event if it is clearly unrelated to INXN-2001 injection (eg, accidental trauma). If an AE associated with injection cannot be definitely shown to be unrelated to INXN-2001, then study stopping rules will apply.

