7.2.2 Determination of Severity

The severity of AEs will be assessed according to the NCI CTCAE, v. 4.03. If the AE is not defined in the NCI CTCAE, v. 4.03, the investigator will determine the severity of an AE based on the following definitions:

- Mild (Grade 1): The AE is noticeable to the subject, but does not interfere with routine activity. The AE does not require discontinuing administration or reducing the dose of the study drug.
- Moderate (Grade 2): The AE interferes with routine activity, but responds to symptomatic therapy or rest. The AE may require reducing the dose, but not discontinuing administration of the study drug.
- Severe (Grade 3): The AE significantly limits the subject's ability to perform routine activities despite symptomatic therapy. In addition, the AE leads to discontinuing administration or reducing the dose of the study drug.
- Life Threatening (Grade 4): The AE requires discontinuing administration of the study drug. The subject is at immediate risk of death.
- Death (Grade 5): The subject dies as a direct result of the complication or condition

Adverse events should be reported using the maximum intensity of the event (eg, if a subject reported nausea lasting 3 days, 1 start date and stop date should be recorded along with the maximum intensity experienced for that event over that 3-day timeframe).

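### A treatment-related Grade 4 injection-site reaction or Grade 4 hematologic toxicity has two incompatible instructions (6.2.5 closing paragraph against Tables 4 and 3), and 5.3 does not settle which applies

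*Protocol*

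**What the plan says.** Four places in the protocol bear on what happens after a severe related event.

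- **5.3 (withdrawal).** A subject must "be withdrawn in the event of any of the following", and one listed item is "Any treatment-related AE meeting withdrawal criteria". The section gives no grade, no criteria and no cross-reference.
- **6.2.5, closing paragraph.** The rule covers "Subjects who experience a treatment-related Grade 4 AE, other than nausea and/or vomiting in the absence of optimal treatment with antiemetics", and its stated action is that they "will be discontinued from study treatment". The next sentence makes an exception: if "the subject has experienced a substantial benefit from treatment and the PI and Medical Monitor recommend continuation on the study", the paragraph goes on to say that "re-exposure to the experimental treatment may proceed on a case-by-case basis". The only event type carved out of the paragraph is the nausea and vomiting named in its first sentence.
- **6.2.5, Table 3.** This table covers palifosfamide-related toxicity. Its row for Grade 4 hematologic toxicity of any kind delays palifosfamide by up to 14 days until recovery and then reduces the dose by 20%. It does not call for discontinuation.
- **6.2.6, Table 4.** This table covers injection-site reactions only. Its Grade 4 row reads "Permanently discontinue study treatment and notify Medical Monitor", with no exception and no reference to 6.2.5.

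**The concern.** A site facing one of these events should find one instruction. For a related Grade 4 injection-site reaction in a subject who appears to benefit, one passage ends treatment for good and another lets it resume. For a related Grade 4 hematologic toxicity in Arm C, one passage keeps the subject on palifosfamide at a reduced dose and another takes the subject off study treatment.

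Safety and tolerability by arm is a primary objective, and the choice of passage feeds the data behind it. It affects cumulative exposure. It moves the treatment-emergent window, which under 8.4.4 runs to the safety visit 28 days after the last dose. It also affects replacement: under 5.4, a subject who stops before six cycles for a reason other than progression may be replaced. Finally, 8.6.1 summarizes major protocol violations by arm, and it is unclear whether a re-dosed subject would be one of them.

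**Working it through.** No arithmetic applies, because the point rests on no sample size, rate or error level. The check is to take each event type and read every passage that covers it.

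**1. Related Grade 4 injection-site reaction, substantial benefit judged present.**
- Table 4, Grade 4 row: stop permanently.
- 6.2.5 closing paragraph: stop, but re-exposure is possible if the investigator and Medical Monitor recommend continuing. The event is treatment-related and Grade 4 and is not nausea or vomiting, so it falls within the paragraph.
- The two cannot both be followed if continuation is recommended. The word for permanent appears in the Grade 4 row and not in the Grade 3 row of the same table, so it does not look accidental. Both arms receive INXN-2001, so both are exposed to this conflict.

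**2. Related Grade 4 hematologic toxicity, Arm C.**
- Table 3: delay palifosfamide, then continue at a reduced dose. No judgment of benefit is required.
- 6.2.5 closing paragraph: discontinue study treatment, with a return only through the benefit exception.
- The table's title limits it to palifosfamide-related toxicity, so the row includes treatment-related events. The Grade 3 and Grade 4 non-hematologic rows are expressly limited to events that are not treatment-related, which keeps them clear of the closing paragraph. The hematologic row has no such limit.

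**3. Does 5.3 decide between them?** It requires withdrawal only when criteria are met, and it does not say which. If the criteria are those of Table 4, the subject in step 1 must be withdrawn. If they are those of 6.2.5 with its exception, that subject need not be. The same uncertainty applies to step 2. So 5.3 carries both conflicts forward without resolving either.

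**4. Any other related Grade 4 event.** Table 4 and the Table 3 hematologic row do not apply. The closing paragraph of 6.2.5 gives a rule and its own exception, and 5.3 can be read consistently with it. What remains here is a missing cross-reference, not a contradiction.

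**The case against.** The strongest reply is that a specific rule displaces a general one. Table 4 was written for injection-site reactions and the Table 3 row for hematologic toxicity, so each would override the closing paragraph. That is a natural reading, but the protocol does not state it. Section 6.2.6 also describes the Table 4 actions as recommended, while the closing paragraph of 6.2.5 is worded as a directive. A site could reasonably rank them either way.

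A second reply is that the Medical Monitor is involved on both routes in the injection-site case: notified under Table 4, and a party to the recommendation under 6.2.5. This stands in part and makes divergence between sites less likely. It does not help with the Table 3 row, which names no such contact.

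Three stronger readings are tempting, and the documents do not support them.
- A reader might infer that 5.3 mandates withdrawal for every treatment-related adverse event. It does so only for those meeting withdrawal criteria.
- A reader might infer that Table 4 makes discontinuation permanent for all Grade 4 events. It covers injection-site reactions alone.
- A reader might count 7.2.2 as a further conflicting rule, because its Grade 4 entry says "The AE requires discontinuing administration of the study drug". That scale is a fallback for events that CTCAE v4.03 does not define, and 6.2.6 grades injection reactions by CTCAE v4.03. It therefore does not govern the injection-site case, and it defines severity, not management.

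**Conclusion.** The point holds for two event types: a related Grade 4 injection-site reaction in a subject judged to benefit substantially, and a related Grade 4 hematologic toxicity in Arm C. In each, two current passages give instructions that cannot both be followed, and neither 5.3 nor any other section ranks them. This is an inconsistency in stated safety rules, not a flaw in the trial design.

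No subject count should be attached. A reader might try to build one from an assumed rate of related Grade 4 events and the 15% to 65% span of the planning values for 16-week progression-free survival. Such a count would cover related Grade 4 events well beyond the two types in conflict, and those planning values do not measure benefit as judged when an event occurs. An effect on the by-arm safety results is possible, but the documents do not demonstrate one.

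The conclusion assumes that the Table 3 hematologic row covers treatment-related events, as the table's title indicates, and that no precedence rule stands in text removed from the public version.

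**What to change.** In one amendment:

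1. Reconcile Table 3, the closing paragraph of 6.2.5 and Table 4 so that one rule, with a stated precedence, applies to treatment-related Grade 4 events.
2. State whether the re-exposure exception in 6.2.5 reaches injection-site reactions.
3. State how the Grade 4 hematologic row of Table 3 relates to the discontinuation rule in the closing paragraph.
4. Have 5.3 name the section that holds its withdrawal criteria.

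Which rule should hold in each case is a clinical decision for the sponsor's team, and this review takes no position on it. The cost is amendment wording. It adds no procedures or subjects. No new safety table is needed either, since 8.4.4 already plans to present event timing relative to dosing and case-by-case narratives for related serious events.
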